6.5.13 Pharmacodynamic Biomarker Analyses

Complement functional activity in serum and CSF measured as CH50 values estimated by the sheep RBC hemolysis assay and plasma and CSF C5 levels measured by ELISA will be summarized by treatment group and visit in the ERO sample. Summary statistics will be provided for the values, change from baseline, and percent change from baseline at each scheduled assessment time point.

Population pharmacodynamic or population pharmacokinetic/pharmacodynamic analyses may be conducted. Details of such analyses will be described in a separate DAP and will be performed by UCB Ra Pharma. The results of the analyses will be reported in a separate report and will not be reported in the CSR.

6.6 Safety Analyses

6.6.1 Treatment-emergent Adverse Events

Summaries and analyses of treatment-emergent adverse events (TEAE) are the same as specified in the M-SAP with the following revisions.

TEAEs are defined as those adverse events with onset dates in the interval from double-blind treatment initiation to the earliest of the Final Safety Visit, the date the participant dies, early terminates, or is lost to follow-up, 40 days after last dose of study drug, or the date of first dose of study drug during participation in the OLE, if so exposed. Adverse events with onset on the day of double-blind treatment initiation and adverse events with incompletely specified onset date where the ambiguous date spans the day of double-blind treatment initiation or the earliest of the events above that define the end of the treatment-emergence interval will be assumed to be treatment emergent except for those known to precede first exposure to study drug.

In addition to summaries specified in the M-SAP, all adverse events, including those not classified as TEAEs, will be summarized by Medical Dictionary for Regulatory Activities (MedDRA) system organ class and preferred term and serious TEAEs will be summarized by MedDRA system organ class, high level term, and preferred term for all TEAEs. In addition, TEAEs will be summarized by MedDRA system organ class and preferred term for fatal TEAEs, TEAEs that occurred during a participant's COVID-19 infection (defined as 5 days prior to symptom onset to end of COVID-19 symptoms or the earlier of 91 days after symptom onset or the end of double-blind follow-up, if ongoing), TEAEs of interest, TEAEs of interest stratified by severity, serious TEAEs of interest, and TEAEs and serious TEAEs stratified by the following subgroups: baseline riluzole use, baseline edaravone use, age, sex, race, ethnicity, weight, BMI, and CKD stage. Subgroup classifications will be the same as described in Section 6.5.10 Subgroup Analyses except that the "other" group will be retained regardless of prevalence.

TEAEs indicating COVID-19 infection are the following: Asymptomatic COVID-19, COVID-19, COVID-19 pneumonia, COVID-19 treatment, Post-acute COVID-19 syndrome, SARS-CoV-2 antibody test positive, SARS-CoV-2 RNA increased, SARS-CoV-2 sepsis, SARS-CoV-2 test false negative, SARS-CoV-2 test positive, SARS-CoV-2 viraemia, Suspected COVID-19. TEAEs of interest are defined in Appendix 1 of this R-SAP.

Treatment-dependent differences in the proportion of participants experiencing a given type of TEAE will not be tested. Treatment-dependent differences in TEAE incidence rates in units of number per 100 participant years will be estimated as differences rather than ratios and will include comparison-wise 95% confidence intervals with variance estimates obtained by the delta method.

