-42 to -1 Days	-41 to -14 Days	Day 0	Day 14 ±3	Day 28 ±7	Day 56 ±7	Day 84 ±3	Day 112 ±7	Day 140 ±3	Day 168 ±7	Day 40d ±3 after last dose	X	Day 14 ±3	Day 28 ±7	Day 56 ±7	Day 84 ±3	Day 112 ±7	Day 140 ±3	Day 168 ±3	q12w ±14d	
Uninstall Smartphone App	Regimen																			
Assignment to the Regimen	Master	X																		
Randomization within the Regimen	Master			X																
Administer/ Dispense Investigational Product (IP)	Regimen			X ⁹		X	X	X	X ¹⁴			X	X	X					X ²⁷	
IP Accountability/ Compliance	Master				X ²⁸	X	X	X ²⁸	X	X ²⁸	X	X ²⁸	X	X	X ²⁸	X	X ²⁸	X ²⁸	X	
Exit Questionnaire	Master										X									
N. meningitidis Vaccination ¹⁰	Regimen		X			X	X										X ¹⁰			
Vital Status Determination ¹⁷	Master										X ¹⁷									

1. Master Protocol Screening procedures must be completed within 42 days to 1 day prior to Baseline Visit.
2. During the Master Protocol Screening Visit, participants will be consented via the Master Protocol informed consent form (ICF). After a participant is randomized to a regimen, participants will be consented a second time via the regimen-specific ICF.
3. At the Regimen Specific Screening Visit, participants will have regimen-specific inclusion and exclusion criteria assessed.
4. Vital signs include weight, systolic and diastolic pressure, respiratory rate, heart rate and temperature. Height measured at Master Protocol Screening Visit only.
5. Clinical safety labs include hematology (CBC with differential), complete chemistry panel, thyroid function and urinalysis. Serum pregnancy testing will occur in women of child-bearing potential at the Master Protocol Screening Visit and as necessary during the study. Pregnancy testing is only repeated as applicable if there is a concern for pregnancy.
6. Adverse events that occur after signing master protocol consent form will be recorded.

7. The DNA sample can be collected after Baseline Visit if a baseline sample is not obtained or the sample is not usable.
8. In addition to study visits outlined in the SOA, participants will be asked to complete twice weekly voice recordings at home. During weeks when a participant is doing a voice recording in-clinic, he or she would only do one other voice recording at home that week.
9. Administer first dose of investigational product (IP) only after Baseline Visit procedures are completed

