5.10 Zilucoplan Known Potential Risks and Benefits

5.10.1 Known Potential Risks

There are potential benefits and risks with the administration of any new investigational medicine as the effects are not fully known. To date, zilucoplan has shown good tolerability and a favorable safety profile across studies as described in the current version of the IB.

It is well established that inhibition of C5 and the terminal complement pathway increases the susceptibility to infection with encapsulated bacteria, in particular *N. meningitidis*. This risk is also described in the prescribing information for eculizumab (Soliris® USPI 2017). Given the increased risk for *N. meningitidis* with C5 inhibition or deficit, patients who participate in zilucoplan clinical trials will be required to have documentation of *N. meningitidis* vaccination (and booster if appropriate) prior to study entry. In addition, while on treatment with zilucoplan, participants will be monitored closely for signs and symptoms of *N. meningitidis* infection. More information on the safety profile of zilucoplan can be found in the IB.

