This Regimen-specific Statistical Analysis Plan (R-SAP) for the zilucoplan regimen (RGA) specifies any modification from the default outcome measures, analysis samples, and planned analyses for the placebo-controlled period of the HEALEY ALS Platform Trial as specified in the Master SAP (M-SAP). The M-SAP and this R-SAP supplement the Master Protocol, the "ALS Master Protocol Recommended Statistical Analysis, Design and Simulation Report" (Appendix 1 to the Master Protocol), and the RGA Regimen-specific Appendix (RSA). Please refer to the Master Protocol and the RGA RSA for details on the rationale for the study design, eligibility criteria, conduct of the trial, clinical assessments and schedule of assessments, definitions and reporting of adverse events, data management conventions, and regulatory oversight and compliance procedures. The "ALS Master Protocol Recommended Statistical Analysis, Design and Simulation Report" (MPRDR) and any regimen-specific deviations described in the RGA RSA and this R-SAP are authoritative in defining the primary and interim analyses. In case of discrepancies between the RGA RSA and this R-SAP concerning use of shared placebos, this R-SAP is authoritative. In case of discrepancies between either SAP and the Master Protocol and the RGA RSA concerning matters of analysis other than the primary and interim analyses and use of shared placebos, the M-SAP and this R-SAP are authoritative. In case of discrepancies between the M-SAP and this R-SAP, this R-SAP is authoritative. On all matters not related to analysis, the Master Protocol and the RGA RSA are authoritative. The following table describes relationships among the relevant documents in adjudicating possible discrepancies with higher numbers indicating greater authority.

Issues potentially requiring adjudication	Master Protocol	RGA RSA	MPRDR	M-SAP	RGA R-SAP
Use of shared placebos	1	4	2	3	5
Primary and interim analysis specifications not related to use of shared placebo	1	5	4	2	3
Statistical analysis specifications not related to use of shared placebo or primary and interim analyses	1	3	2	4	5
All matters not related to statistical analysis	4	5	1	2	3

2. Study Design

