¹¹ Clinical safety labs include hematology (CBC with differential), complete chemistry panel, liver function tests, thyroid function, and urinalysis. Serum pregnancy testing will occur in women of child-bearing potential at the Master Protocol Screening Visit and as necessary during participation. Pregnancy testing is only repeated as applicable if there is a concern for pregnancy.

¹² Blood for PK and PD samples and blood and urine for biomarker samples should be obtained prior to the first daily dose of study drug at each applicable clinic visit.

¹³ If the participant consents to DNA sample collection but a DNA sample is not obtained at the Baseline Visit or if that sample is not usable, a DNA sample can be collected after the Baseline Visit.

¹⁴ If the participant consents to CSF sample collection but a CSF sample is not obtained at the Week 16 Visit, a CSF sample can be collected at the Week 24 Visit.

¹⁵ Adverse events that occur after signing the RGA ICF will be recorded.

¹⁶ Two smartphone apps should be installed on the participant's phone, one to collect home spirometry and one to collect voice recordings.

¹⁷ In addition to study visits specified in the SoA for collection of voice recordings, participants should complete twice weekly voice recordings at home. During weeks when a participant completes a voice recording in-clinic, he or she should only complete one other voice recording at home.

¹⁸ Administer first dose of investigational product only after Baseline Visit procedures are completed.

¹⁹ Drug accountability will not be done at phone visits. A drug compliance check-in should be held during phone visits to ensure participant is taking drug per dose regimen and to note any report of missed doses.

²⁰ Initial administration of conjugate and serotype B meningococcal vaccines must occur at least 14 days prior to the Baseline Visit. Participants must not start study drug until 14 days after initial administration of conjugate and serotype B meningococcal vaccines.

²¹ Vital status, a determination of date of death or death equivalent or date last known alive, will be made for each randomized participant at the end of their double-blind follow-up (generally the Week 24 Visit as indicated) and again, if previously alive, after the end of double-blind follow-up of all participants randomized to RGA. Vital status may also be ascertained at later time points by using publicly available data sources.

3. General Considerations for Data Analysis

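### SAP 6.6.1 defines treatment-emergent adverse events by onset date alone, with no clause for events that begin before the first dose and worsen on treatment

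*SAP*

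**What the plan says.** SAP section 6.6.1 opens with "Summaries and analyses of treatment-emergent adverse events (TEAE) are the same as specified in the M-SAP with the following revisions". The first revision is the definition itself: "TEAEs are defined as those adverse events with onset dates in the interval from double-blind treatment initiation", ending at the earliest of several listed points, one of which is 40 days after the last dose. Events that start on the day of the first dose, or whose partial date spans a boundary of the interval, "will be assumed to be treatment emergent except for those known to precede first exposure to study drug". Increase in severity, seriousness and outcome play no part in the definition.

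Pre-dose events are on record. The regimen appendix (Schedule of Activities, footnote 6) states "Adverse events that occur after signing master protocol consent form will be recorded". The SAP (section 2.9, footnote 15) gives a later start: "Adverse events that occur after signing the RGA ICF will be recorded". Both precede the first dose.

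On precedence, SAP section 1 states "In case of discrepancies between the M-SAP and this R-SAP, this R-SAP is authoritative". The same section sends the reader to the Master Protocol and the regimen appendix for "definitions and reporting of adverse events, data management conventions, and regulatory oversight and compliance procedures".

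On the expected risk, protocol section 5.10.1 states "It is well established that inhibition of C5 and the terminal complement pathway increases the susceptibility to infection with encapsulated bacteria".

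**The concern.** A TEAE definition usually has two limbs: new onset after the first dose, and worsening after the first dose of something already present. Section 6.6.1 has only the first. It is careful about first-day and partial onset dates, so the missing second limb is easy to overlook.

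What is at stake is the safety endpoint itself. Protocol section 2.1 frames it in terms of treatment-emergent adverse and serious adverse events, and infections are the first TEAE of interest in SAP Appendix 1. Suppose a participant has a mild infection at the first dose and it becomes severe or fatal under C5 inhibition. If the record keeps its pre-dose onset date, the event is absent from the tables a reader would consult first for the drug's named risk.

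**Working it through.** The plan gives no figure to reproduce here. The check is a reading of the text, followed by tracing one event through the specified outputs.

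**Step 1. Is there a worsening clause?** No. In the two supplied documents, worsening is mentioned only for efficacy endpoints (SAP 6.5.2 and 6.5.3).

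**Step 2. Could the Master SAP supply one?** It cannot be assumed to. Section 6.6.1 presents its definition as a revision of the Master SAP, and section 1 lets the regimen SAP prevail where they differ.

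**Step 3. Can affected events exist?** Yes, but the window varies.
- Upper bound: Master Protocol screening may start 42 days before Baseline. Against 168 days of treatment that is 42 / (42 + 168) = 20.0% of collection time.
- Where initial meningococcal vaccination is needed: at least 14 days, so 14 / (14 + 168) = 7.7%.
- Lower bound: SAP section 2.9, footnote 2, allows regimen screening on the Baseline day when initial vaccination is not needed. With recording from regimen consent (footnote 15), the window can be about 0 days.

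These are shares of time. They say nothing about how often events worsen, and they leave out the post-dose follow-up.

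**Step 4. Trace an event with a known pre-dose onset that becomes serious on treatment.**

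| Output | Does it capture the event? |
|---|---|
| Serious, fatal, of-interest and subgroup TEAE tables (SAP 6.6.1, Appendix 1) | No, if the original onset date is kept |
| Differences in TEAE rates per 100 participant-years (6.6.1) | No, on the same condition |
| TEAEs by antibody status (Appendix 2) | No, on the same condition |
| Summary of all adverse events by organ class and preferred term (6.6.1) | Yes, but no split by seriousness, fatality or worsening is stated |
| Time to first hospitalization for an SAE, with death or death equivalent in the composite (5.11, 6.5.4) | Yes, if hospitalized or fatal; time runs from Baseline with no onset restriction |
| Survival analyses and listings (6.5.4), deaths in disposition (6.7.1) | Deaths only; no link to the adverse event is specified |
| Laboratory shift tables (6.6.2) | Laboratory changes only |

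If the worsening is instead entered as a separate record with an onset after the first dose, that record is a TEAE under the rule as written.

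**Step 5. Size.** The documents give no rate of pre-dose events or of worsening. As an illustration only, on assumptions that are not in the documents: 0.3 to 0.6 pre-dose events per participant, 30% to 50% ongoing at the first dose, and 10% to 20% of those worsening.
- Per participant: 0.3 × 0.3 × 0.1 = 0.009 to 0.6 × 0.5 × 0.2 = 0.06.
- Active arm, 120 participants: 1.1 to 7.2 events.
- Regimen placebo, 40 participants: 0.4 to 2.4 events.

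These cover adverse events of every kind. Serious infections would be a smaller part, which cannot be estimated from the documents. The finding does not depend on these counts.

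**The case against.** The strongest reply is that the answer may lie in a document not supplied. Adverse event definitions and reporting conventions are referred to the Master Protocol as well as the regimen appendix. If the Master Protocol tells sites to enter worsening as a new event, section 6.6.1 already counts it. This stands, and it makes the consequence conditional. It does not remove the point, because section 6.6.1 neither states nor cites such a convention.

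A second reply is that the outcomes that matter most are analysed elsewhere. This stands in part. An infection already present at the first dose that leads to hospitalization or death falls within the time-to-event analyses, which run from Baseline in several analysis sets. Progression to a new diagnosis may also be recorded as a separate event. What is left is worsening without hospitalization or death, together with the attribution of serious and fatal events in the TEAE tables.

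A reader might infer more than the text supports:
- That such events can never be treatment-emergent. This depends on the recording convention.
- That the regimen SAP removed a worsening clause from the Master SAP. The Master SAP was not available, so what it says is unknown.
- That a difference between arms would be invisible everywhere. The outputs in Step 4 show otherwise.
- That the rule can only hide harm. It applies to both arms, and omitting worsening on placebo could equally hide a benefit.
- That every participant has a pre-dose window of at least 14 days that includes vaccination. SAP section 2.9 allows otherwise.

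**Conclusion.** The point holds as a gap in the definition. Section 6.6.1 uses onset date only and does not deal with pre-existing events that worsen on treatment. Where worsening is kept under the original pre-dose onset, it is missing from the TEAE tables and rate differences in both arms, and those outputs cannot show a between-arm difference in worsening. That conclusion rests on one unverified condition: that worsening is not already entered as a new event.

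The loss is partial, because hospitalizations, deaths and the summary of all adverse events remain. Its size cannot be derived from the documents. It merits correction because infection is both the drug's named risk and the first TEAE of interest, and because the correction is small.

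**What to change.** In SAP section 6.6.1, define a TEAE as either an adverse event with onset in the stated interval, or an adverse event with earlier onset that increases in severity, becomes serious or becomes fatal in that interval. Date the second kind at the worsening, or at the date of seriousness or death if only that is held. Where the worsening is already entered as a separate record, count it once. Apply the definition to every TEAE table, including the of-interest and antibody-status tables, and to the rate differences. If the Master Protocol already requires a new record for worsening, cite that rule in section 6.6.1.

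The start of adverse event recording should also be made the same in the regimen appendix (footnote 6) and the SAP (section 2.9, footnote 15), since it decides which pre-dose events are on record.

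The cost is one sentence and one derived flag, with two limits. The supplied documents do not show that dates of severity change are collected; without them, a non-serious, non-fatal increase in severity cannot be dated, and the SAP should say so. Some natural ALS worsening will also be counted as treatment-emergent, in both arms.

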Zilucoplan shows species selectivity for non-human primate and human complement C5 only. The primary pharmacology of zilucoplan was established in vitro using direct binding and functional inhibition of complement assays, as well as enzyme-linked immunosorbent assays (ELISAs). Using surface plasmon resonance and analysis of a high-resolution co-crystal structure, zilucoplan has been shown to bind to a specific site on C5 and to exhibit a strong and rapid association with C5, as well as a slow dissociation rate. The binding site is distinct from that of the complement C5 inhibitor monoclonal antibody eculizumab and therefore is not affected by mutations in complement C5 known to prevent binding of eculizumab in patients of Asian and Han-Chinese descent (Nishimura et al. 2014). Target (C5) binding was confirmed using a competitive ELISA employing biotinylated zilucoplan to capture C5. Additionally, zilucoplan demonstrated dose-dependent inhibition of C5a and C5b formation following activation of classical or alternative pathways, as well as inhibition of RBC lysis in serum/plasma. Zilucoplan is a potent complement inhibitor in primates and humans and a weak/poor inhibitor in all other animal species tested (see below).

[figure not shown]
Species	IC ₅₀ (nM)
Human	6.6
Non-human primate	
Baboon	5.2
Chimpanzee	11.7
Cynomolgus	3.5
Rhesus	17.6
Dog	> 4,700
Rabbit	> 67,000
Porcine	
Mini-pig	51.9
Pig	118.6
Rodents	
Mouse	> 36,000
Rat	591.2
Guinea Pig	> 100,000

Table 1: Pharmacological potency of zilucoplan (IC₅₀) in species tested

Zilucoplan is slowly absorbed in preclinical species after single SC administration, with mean T_{max} ranging from approximately 5 to 8 hours post-dose. The mean elimination half-life in plasma is 7 days in monkeys and humans. The slow elimination kinetics are largely driven by high affinity interaction with the target protein C5 and a much lower affinity interaction with albumin and other plasma proteins. Metabolism of zilucoplan is well-characterized and studies have identified two primary metabolites that occur in similar ratios in both monkeys and humans. Excretion of parent and major metabolites is predominantly hepatobiliary.

The PK/PD relationship of zilucoplan has been extensively investigated in cynomolgus monkeys. An EC₉₀ of 2500 ng/mL was determined in monkeys which translated nearly precisely to the clinical experience in generalized myasthenia gravis trials (Figure).

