6.1.11 Process for Early Terminations

Participants who early terminate from the study and do not complete the protocol will be asked to be seen for an in-person Early Termination Visit and complete a Follow-Up Safety Call. If a participant is not able to be seen in-person, safety assessments and others that can be conducted remotely should be performed.

The in-person Early Termination Visit should be scheduled as soon as possible after a participant early terminates. If the participant early terminates during the placebo-controlled portion of the Regimen, all assessments that are collected at the Week 24 in-clinic visit should be conducted. If the participant early terminates during the OLE phase, all assessments that are collected at the OLE Week 52 in-clinic visit should be conducted. The Follow-Up Safety Call should be completed approximately 40 days after the last dose of study drug.

If the Early Termination Visit occurs approximately 40 ± 3 days after the last dose of study drug, the information from the Follow-Up Safety Call can be collected during the Early Termination Visit, and a separate Follow-Up Safety Call does not need to be completed. If the in-person Early Termination Visit does not occur within 40 ± 3 days of the last dose of study drug, the Follow-Up Safety Call should occur approximately 40 ± 3 days after the last dose of study drug and the Early Termination Visit will be completed after the Follow-Up Safety Call.

Note: Participants should be instructed to continue using effective contraception for at least 40 days after their last dose of study drug.

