- Efficacy Per-protocol (EPP) Set: The subset of participants in the FAS analysis set who initiated study treatment and who were not involved in protocol deviations that affected the scientific integrity of the trial as documented prior to data lock, classified according to the treatment they actually received. Inclusion or exclusion from the EPP analysis set of any participant for whom treatment assignment was unblinded prior to data lock will be governed by the prespecified criteria above. If a participant's data is truncated for inclusion in the EPP analysis set due to non-adherence to protocol-specified dosing, clinical events observed up to 40 days after the censoring event will be included in the EPP analysis set. For all other events leading to truncation of a participant's data, no events beyond that date will be included. Data from placebo participants shared from other regimens will not be truncated due to non-adherence to protocol-specified dosing.

Applicable analysis sets (FAS, EPP, and STF) will include shared placebo participants from regimens B, C, and D. Data from shared placebo participants will include visits and events that occurred on or before the date of the final placebo-controlled period follow-up of an RGA participant. As only concurrently enrolling regimens are contributing to efficacy analyses, the FAS and ECC analysis sets are synonymous and only the FAS analysis set will be referenced. As

RGA is the only regimen administering study drug by subcutaneous injection among those contributing to safety analyses, the ECM and ERO analysis sets and the STN and SRO analysis sets are synonymous and only the ERO and SRO analysis sets will be referenced.

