6.7 Other Analyses

6.7.1 Participant Disposition

All participants consented to the Master Protocol between the time of the first and last consent of a participant assigned to a regimen included in the FAS analysis set will be summarized as a single set for the following events: consented to the Master Protocol, failed screening for the Master Protocol, other reasons not assigned to a regimen (including timing out of the screening window, death, withdrawal of consent, early termination, and administrative termination), and assigned to a regimen. Reasons for Master Protocol screen failure will be summarized.

All participants in the above sample assigned to a regimen will be summarized as two sets (final screening for RGA vs. final screening for a non-RGA regimen) for the following events: consented to a regimen, failed screening for a regimen, other reasons not randomized within a regimen (including timing out of the screening window, death, withdrawal of consent, early termination, and administrative termination), and randomized within a regimen. If a given individual is screened multiple times prior to randomization within a regimen, then the final screening experience of that individual will be summarized. Reasons for RGA screen failure will be summarized separately for all participants screened for RGA whether that was their final screening experience or not.

All participants in the FAS analysis set will be summarized as two sets (randomization to active study drug vs. randomization to placebo) for the following events: initiated regimen-specific study drug, prematurely terminated study participation due to death, withdrawal of consent, early termination, loss to follow-up, or administrative termination, completed 24-week follow up, and

completed a safety follow-up visit vs. continued into the OLE. Reasons for withdrawal of consent or early termination after randomization will be summarized.

Any randomized participants excluded from the FAS and EPP analysis sets or included in the FAS analysis set but not contributing to the primary analysis will be identified in a listing together with the reason for their exclusion.

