6.7.2 Study Drug Compliance and Tolerance

Summaries of study drug compliance and tolerance are the same as specified in the M-SAP with the clarification that summaries will be reported for the ERO and SRO analysis sets and that date of permanent discontinuation of study drug is the date of last use of double-blind study drug among all participants in a given analysis set.

The number of days of exposure to study drug will be calculated in three ways:

- as the number of days from dose initiation to the final safety assessment during the placebo-controlled period, inclusive,
- as the number of days from dose initiation to drug withdrawal, inclusive, less any interval during which use of study drug was interrupted (individual missed doses will not be subtracted unless noted in the dosage management log), and
- as the number of days from dose initiation to the earlier of final contact during the placebo-controlled period or 40 days after last dose of study drug, inclusive.

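### SAP 6.6.1 closes the TEAE interval at early termination, so AEs that start after it but within 40 days of last dose are collected yet not counted as TEAEs, unless termination means last safety contact

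*SAP*

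**What the plan says.** SAP 6.6.1 classifies by onset date. The interval opens at first double-blind dose and runs "to the earliest of the Final Safety Visit, the date the participant dies, early terminates, or is lost to follow-up, 40 days after last dose", or to first OLE dose. Early termination is a separate limb, and the first date reached governs. An incomplete onset date that spans the cut-off is taken as treatment-emergent.

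The same section says that "all adverse events, including those not classified as TEAEs, will be summarized" by system organ class and preferred term. The serious, fatal and of-interest tables are built from TEAEs. On rates it says: "Treatment-dependent differences in TEAE incidence rates in units of number per 100 participant years will be estimated as differences rather than ratios". It does not name the denominator.

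On sequence, Protocol 6.1.11 says: "The in-person Early Termination Visit should be scheduled as soon as possible after a participant early terminates". It also requires a Follow-Up Safety Call about 40 days after last dose, and Protocol 6.1.10 gives documenting AEs as the purpose of that call. Protocol 3.2 describes this route out of the placebo-controlled period as terminating early and also completing the visit and the call.

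Elsewhere the SAP uses 40 days after last dose with no cut at early termination. Sections 6.6.2 to 6.6.6 do so for laboratory, ECG, vital-sign, suicidality and post-baseline immunogenicity data. The third exposure definition in 6.7.2 counts days from dose initiation "to the earlier of final contact during the placebo-controlled period or 40 days after last dose of study drug, inclusive".

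**The concern.** If early termination is dated when the participant leaves, the rule discards from the TEAE outputs follow-up that the Protocol deliberately collects. A serious infection starting two weeks after termination, and reported at the day-40 call, would be recorded but would not be a TEAE.

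The outputs affected are the main safety ones: serious, fatal and of-interest TEAEs, the TEAE rates, and the TEAE summaries by antibody status in SAP Appendix 2. Appendix 1 lists Neisseria infections as events of interest, and Protocol 5.10.1 treats greater susceptibility to them under C5 inhibition as established. The days cut off directly follow the last dose, when residual drug is highest.

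The windows also disagree. Suppose a participant terminates on the day of last dose and attends the Early Termination Visit 20 days later. The laboratory results from that visit are tabulated, but an AE starting that day is not a TEAE.

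**Working it through.** The plan gives no figure to reproduce, so the check is date arithmetic.

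**Inputs.** The 40-day window is from SAP 6.6.1 and the call timing from Protocol 6.1.11. For the half-life, Protocol 3.1 states: "The mean elimination half-life in plasma is 7 days in monkeys and humans". The gap g, in days from last dose to early termination, is not given, so it is varied. Assumptions: the participant is alive, outside the OLE and reachable to day 40, and drug declines by first-order elimination.

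**Formulas.**
- Interval end as written = min(last dose + g, last dose + 40).
- Days lost = max(0, 40 − g).
- Drug level left at termination = 2^(−g/7).
- Share of day 0–40 residual exposure lying in the lost days = (2^(−g/7) − 2^(−40/7)) / (1 − 2^(−40/7)), with 2^(−40/7) = 1.9%.

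The example column assumes last dose on day 84 and the call on day 124.

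| g (days) | Interval ends (day) | Days lost | Level left at termination | Share of residual exposure lost |
|---|---|---|---|---|
| 0 | 84 | 40 | 100% | 100% |
| 14 | 98 | 26 | 25% | 23.5% |
| 28 | 112 | 12 | 6.25% | 4.4% |
| 40 or more | 124 | 0 | 1.9% or less | 0% |

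**Scale.** No termination rate is given, so no trial total can be derived. For every 10 affected participants the loss is 10 × 40 / 365.25 = 1.10 participant-years at g = 0, 10 × 26 / 365.25 = 0.71 at g = 14, and 10 × 12 / 365.25 = 0.33 at g = 28. These are days of observation, not events.

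**Rates.** The effect depends on the unstated denominator. If it is the third exposure definition in 6.7.2, a participant terminating at last dose on day 84 has a TEAE window of 84 out of 84 + 40 = 124 counted days, or 68%. With last dose on day 28 it is 28/68 = 41%, and on day 140 it is 140/180 = 78%. If the denominator is also cut at termination, there is no mismatch, although the events still leave the TEAE tables.

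**Who is affected.** Only participants who leave less than 40 days after last dose. Those who stop drug but stay on study are not touched by this limb. SAP 6.7.1 lists participants who "prematurely terminated study participation due to death, withdrawal of consent, early termination, loss to follow-up, or administrative termination", so early termination may be only one of several ways of leaving early.

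**The case against.** The strongest objection is that the meaning of the limb rests on documents not supplied. SAP 6.6.1 revises the Master SAP, and SAP 2.4 refers follow-up procedures to it and to the Master Protocol. Protocol 3.2 can be read as ending participation only once the visit and call are complete, and SAP 6.7.1 treats early termination as an end of study participation. If the recorded date is that end date, nothing is lost. This stands as a real alternative. It does not settle the matter, because Protocol 6.1.11 puts the visit after termination and neither supplied document defines the date. SAP section 1 also ranks this SAP above the Master SAP, so a different Master SAP window would not prevail; only a definition of the term would help.

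A reader might infer more than the documents support:

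- *That every AE collected after termination is lost.* Status follows onset. An event first reported at the call but begun on or before termination is still a TEAE.
- *That the events vanish.* They stay in the all-AE table. SAP 6.5.4 lists deaths in the STF and SRO sets and analyses time to SAE hospitalization there, and the censoring rules in 5.11 do not name early termination.
- *That the per-protocol rule proves 40 days was intended.* SAP 6.1 says "clinical events observed up to 40 days after the censoring event will be included in the EPP analysis set", but only for truncation due to dosing non-adherence. Its next sentence applies a same-day cut to all other truncations, and this is an efficacy set.
- *That sections 6.6.2 to 6.6.6 prove an error.* Most of those data are tied to visits, so the difference shows inconsistency only.
- *That TEAE rates are biased.* The denominator is unstated and the rule is the same in both arms.

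It is also fair that a gap of zero is the extreme case and that drug level is not event risk.

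**Conclusion.** The point holds as a conditional one. In the Protocol's own usage, the early-termination limb removes from the TEAE outputs any AE with onset after termination and within 40 days of last dose, although the Protocol requires those AEs to be collected. The cost is up to 40 days per affected participant, falling to zero at a gap of 40 days. With the stated half-life and first-order decline, the lost days hold all of the day 0–40 residual exposure at a gap of 0, about a quarter at 14 days and about 4% at 28 days.

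The total is unknown, no direction of bias between arms is claimed, and an under-counted rate follows only under some choices of denominator. Confidence is medium, because a Master SAP definition of the termination date as last safety contact would remove the loss. The limb should still be corrected: it governs the main safety tables, and the correction is small.

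**What to change.** In SAP 6.6.1, replace the early-termination limb with the date of last safety contact, defined as the later of the Early Termination Visit and the Follow-Up Safety Call, if completed. Where neither takes place, use the last contact at which AEs were reviewed. The interval then ends at the earliest of last safety contact, death, loss to follow-up, 40 days after last dose, or first OLE dose. This also does the work of the Final Safety Visit limb, which this SAP leaves undefined. Add one sentence stating that the TEAE-rate denominator stops at the same date.

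Simply deleting the limb is not enough: a participant who has terminated and cannot be reached, but is not classed as lost to follow-up, could then be credited with unobserved time up to day 40. If the Master SAP already dates termination at last safety contact, a cross-reference in 6.6.1 suffices, plus the denominator sentence.

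The cost is two sentences and a change to the TEAE flag, with no new data. The downside is that some post-treatment events of ALS progression will count as TEAEs, as they already can for completers followed to the 40-day call.
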